# **Study Summary**

Title	COVID-FIS: A Phase 2 Placebo-Controlled Pilot Study in COVID-19 of Fisetin to Alleviate Dysfunction and Excessive Inflammatory Response in Older Adults in Nursing Homes	
Running Title	COVID-FIS: COVID-19 Pilot Study of Fisetin to Alleviate Dysfunction and Inflammation	
Protocol Number	20-008867	
Phase	Phase II	
Methodology	Randomized, placebo-controlled, double-blind secondary prevention trial	
Overall Study Duration	32 months	
Subject Participation Duration	Subject participation duration 6 months (screening, 4 days treatment, follow-up visits, unblinded at the end of the study)	
Single or Multi-Site	Multi-Site	
Objectives	
 
To prevent COVID-19 (CoV) disease complications by a 7 point score adapted from the WHO Ordinal Scale for Clinical Improvement of CoV (Appendix 1)
 
To evaluate safety and tolerability of Fisetin in this patient population
 
To reduce progression of severity of SARS-CoV-2 infections with no, mild, or moderate to severe or critical symptoms. To decrease senescent cells, inflammation, and physical dysfunction (frailty)
 
	
Number of Subjects	250 enrolled and screened, 150 accrued and randomized	
Diagnosis and Main Inclusion Criteria	Women or men age $\geq$ 65 years in a nursing home with mRNA-PCR test-proven CoV infection. SpO2 $\geq$ 85% (on room air or $\leq$ 2 L of supplemental oxygen) at time of enrollment.	
Study Product, Dose, Route, Regimen	This study will involve a 2-day oral or NG or D tube course of Fisetin twice (~20 mg/kg/day for 2 consecutive days; Days 0, 1, 8 and 9).	
Duration of Administration	4 out of 10 days	
Reference therapy	Reference therapy Placebo-controlled	
Statistical Methodology	Assuming 75 subjects/ group with a significance level of 0.05, the study will have 80% power to detect an odds ratio of 2.24 comparing the placebo- to Fisetin-treated group, using the 7-point severity score at Day 14 as the endpoint in an ordinal logistic regression model.	

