# 3.5 Secondary Study Endpoints

In this pilot study of elderly adults in nursing homes who have proven CoV infection and no, mild, or moderate symptoms (Table 4), secondary endpoints will be: 1) safety and tolerability; 2) decreased blood senescent cells (blood CD3+ T cell assay for p16INK4A and SASP factors; if feasible); 3) cognitive function (from MDS section C, Cognitive Patterns, items C0100 – C1310; 4) function status/activities of daily living (from MDS Section G, Functional Status, items G0110-G0900; 5) functional abilities/frailty (from MDS section GG, Functional Abilities and Goals, items GG0130-0170 improved physical and cognitive function; 6) decreased circulating inflammatory markers and mediators (if feasible); 7) prevention or delay of deterioration in oxygenation status (SpO2/FiO2) if feasible; 8) reduced progression to intubation/ transition to end-of-life palliative care because of worsening condition, transfer to special nursing home unit admission because of worsening condition, hospital, ICU admission/ progression to ARDS/ myocarditis with troponin leak, death, delayed recovery, and delayed antibody response, and 9) decreased lung fibrosis during or at the end of the 6 month time subjects are in the study.

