### 4.5. Data Collection and Follow-Up for Withdrawn Subjects

- For withdrawn subjects (due to withdrawal of consent) not undergoing any study intervention, no additional follow-up will be done.
- For withdrawn subjects (due to withdrawal of consent) receiving Fisetin (Intervention), any additional evaluation will be for subject safety only. Research data will not be collected on subjects after withdrawal of consent.

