# 5.6 Prior and Concomitant Therapy

Drugs listed as part of the exclusion criteria are not permitted during each of the two 2 days courses of treatment with Fisetin (Days 0 & 1 and Days 8 & 0). If patients are required to initiate these medications within these periods, then they will be removed from the study primarily due to risk of drug-drug interaction.

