# 8 Statistical Plan

### 8.1 Sample Size Determination

Power calculations for the comparison of the Fisetin and control groups were made assuming an equal distribution among the 7-point scale categories at Day 14 among the controls using a two-sided significance level of 0.05 (alpha). With 75 subjects per group, the study would have 80% power to detect a log odd's ratio of 0.81 which translates to an odd's ratio of 2.25 comparing the control to Fisetin group. Power calculations were run using the PASS software package.

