#### 8.2 Statistical Methods

All participants who are randomized will be included in the primary efficacy analysis. The analysis will follow the ITT principle (*i.e.* according to the treatment arm they are randomized to). For the primary analysis using the values of the 7-point scale, we will test the coefficient of the treatment effect (as a fixed effect) in an ordinal logistic regression model using a 2-sided 0.05 level Wald test after adjusting for key baseline variables such as baseline COVID severity status, age, and sex that show imbalance between the groups. Subjects who withdraw early but received at least some treatment will have their last known values carried forward until they complete the study at Day 180±14. All participants who receive any dose of drug (Fisetin or placebo) will be included in the safety and tolerability evaluation. The definitions of adverse events are described in Sections 9.1-9.3. Participants will be assessed over the entire period of drug administration. Frequency tables will be generated to summarize the occurrence of AE's by treatment arm. Comparisons of the rates of individual AEs will be done using tests of proportions such as the Fisher's exact test or Chi-squared test.

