# **8** Analysis plans for secondary endpoints:

- Rate- or proportion-based endpoints: Several measures will be evaluated in patients that will be summarized as incidence rates or the proportion of patients who have an event or incident of interest; e.g., mortality within 14 days. For these endpoints, we will calculate the proportions of patients who have these incident events of interest for each of the treatment arms and calculate 95% confidence intervals for these outcomes. These will be graphically and quantitatively compared using chi-square tests. Logistic regression models will be used to assess the influence of treatment arm on the incidence of these events while adjusting for other factors of interest.
- Time-to-event endpoints: Similarly, several measures will be analyzed in a secondary manner that will evaluate the distributions of the time to events of interest. These include time to hospital discharge, survival, or symptom improvement. For these outcomes, Kaplan-Meier methods will be used to graphically evaluate potential differences between treatment arms or other groups of interest. Further, these methods will be used to estimate median times as well as time-specific rates (*e.g.*, rate of transfer to hospital at 14 days). Cox proportional hazards models will be used to evaluate the influence of treatment arms, adjusting for other factors of interest.

- Oxygen supplementation and intubation: We will assess the incidence of oxygen supplementation or intubation and time to initiation of oxygen supplementation or intubation. In those who are given oxygen supplementation, we will summarize the duration of oxygen supplementation. Similarly, we will characterize and summarize the need for and duration of intubation. These will be analyzed in a manner similar to that described for the proportion/rate-based variables as well as the time-to-event variables but will specifically be based on a subset of patients given the nature of the outcome of interest. As such, these evaluations will be exploratory in nature.

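### Carrying the last score forward fixes the Day 14 outcome of early withdrawals: a correctable weakness in the primary analysis, not a demonstrated bias

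*Combined protocol and SAP*

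**What the plan says.** The primary analysis compares arms "using the 7-point severity score at Day 14 as the endpoint in an ordinal logistic regression model" (Study Summary). Section 8.2 states: "All participants who are randomized will be included in the primary efficacy analysis". It then adds: "Subjects who withdraw early but received at least some treatment will have their last known values carried forward", through to Day 180. That is the only missing-data rule for the primary endpoint. No imputation model, sensitivity analysis or expected withdrawal rate is given, and 4.4.6 says that participants who withdraw consent are not replaced. The rule gives no value to participants randomised but never dosed (few, since 6.1 asks for same-day dosing where possible). It also does not clearly reach dosed participants lost to follow-up, whom 4.4.2 lists under treatment discontinuation.

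Section 3.5 describes residents "who have proven CoV infection and no, mild, or moderate symptoms". Section 8.1 computes power "assuming an equal distribution among the 7-point scale categories at Day 14 among the controls". The secondary analyses cover time-to-event outcomes: "These include time to hospital discharge, survival, or symptom improvement". The plan thus expects movement in both directions within two weeks.

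On leaving the study, 4.5 says: "Research data will not be collected on subjects after withdrawal of consent". Section 5.6 deals with a participant who must start a listed drug during either two-day course: "then they will be removed from the study primarily due to risk of drug-drug interaction". Section 5.2.3 withdraws participants given mTOR inhibitors, should these become standard of care, unless they are held around dosing.

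**The concern.** A resident who leaves on Day 2 with a good score is analysed as having that score on Day 14. One who leaves at the height of the illness is analysed as never having recovered. If both arms lose participants alike, such errors largely balance. If they do not, the treatment odds ratio picks up a component that reflects who left and when. Its direction depends on disease courses that nobody knows in advance, so carry-forward cannot be defended as conservative. The model also treats each carried score as an observation, so the standard error takes no account of the substitution.

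The two concomitant-drug clauses may add gaps that need not exist, because a resident's score can usually be read from the chart whether or not study drug continues (7.1).

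**Working it through.** **1. The plan's own figure.** Inputs from 8.1: 75 per arm, two-sided 0.05, odds ratio 2.25, controls 1/7 in each category. The proportional-odds formula is n per arm = 6(z₀.₉₇₅ + z₀.₈₀)² / [(ln OR)²(1 − Σp̄³)].

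- (1.960 + 0.842)² = 7.849 and (ln 2.25)² = 0.6576.
- Fisetin-arm probabilities are 0.273, 0.201, 0.154, 0.122, 0.099, 0.082, 0.069. Averaged with 1/7 they give Σp̄³ = 0.0240.
- n = 47.09 / (0.6576 × 0.976) = 73.4 per arm.
- Power at 75 = Φ(√(75 × 0.6418/6) − 1.960) = Φ(0.872) = 80.9%.

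The stated 80% is reproduced. It contains no allowance for withdrawal.

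**2. Direction under no drug effect.** Number the categories 1 (best) to 7 (death). Let m be the mean carried score, μ the mean Day 14 score, and w the withdrawal proportions. If withdrawal is unrelated to outcome, the mean shift (Fisetin minus placebo) is (w_F − w_P)(m − μ). Equal withdrawal gives zero. Take an assumed 15% against 5% (about 11 against 4 of 75):

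- uniform controls, μ = 4, m = 1.5: 0.10 × (1.5 − 4) = −0.25, favouring Fisetin;
- assumed mild distribution 45/20/10/10/2/5/8%, μ = 2.51, m = 1.5: −0.10;
- the same mild distribution, but carried scores averaging 3: 0.10 × (3 − 2.51) = +0.05, against Fisetin.

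**3. Simulation under no drug effect.** Proportional-odds Wald test, 75 per arm, 10,000 trials per setting (standard error about 0.25 points), withdrawal unrelated to outcome, day-to-day noise of one level with probability 0.3. Path sets:

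- A: linear from baseline level 1-2 to the Day 14 level, withdrawal Days 1-8;
- B: final level reached by Day 7;
- C: baseline levels 1-4;
- D: withdrawal Days 1-13;
- E: levels 1-5 peak one or two levels higher at Day 7, then return.

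Type I error in % (mean odds ratio; above 1 favours Fisetin), 5% placebo against 15% Fisetin:

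| Day 14 distribution | A | B | C | D | E |
|---|---|---|---|---|---|
| Uniform (8.1) | 8.4 (1.16) | 6.2 (1.09) | 6.4 (1.09) | 7.0 (1.11) | 5.7 (1.06) |
| Assumed 30/20/10/12/3/5/20% | 6.1 (1.08) | 5.6 (1.04) | 5.1 (1.01) | 5.9 (1.06) | 5.3 (0.99) |
| Assumed mild | 5.3 (1.02) | 5.2 (1.01) | 5.5 (0.95) | 5.2 (1.02) | 6.3 (0.91) |

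At 5% against 10% the ranges are 4.6-5.9% and 0.96-1.08. At 10% in both arms they are 5.1-5.4% and 1.00. Multiple imputation (arm, score at withdrawal, baseline score; 10 imputations; 4,000 trials) on the 15 tabulated settings gives 4.6-5.2% and 0.99-1.01.

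A cruder model draws the carried score without regard to the Day 14 score. At 5% against 15% under uniform controls it gives 12.3% if every carried score is 1 or 2, and 6.6% if they are spread over 1-5. I do not rely on it, because real carried scores follow the patient's course.

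**4. True odds ratio 2.25.** With 10% withdrawal in both arms, carry-forward estimates 2.09-2.23 (2.27 with full data), and imputation changes power by −0.1 to +2.9 points. With 10% placebo against 5% Fisetin under uniform controls, imputation gains from 0.9 points (set E, 76.8 against 75.9%) to 8.8 points (set A, 79.0 against 70.2%). Under the mild distribution carry-forward loses nothing (70.7-75.2% against 69.9-71.9% with imputation).

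**5. The follow-up clauses side by side.** Section 4.4.2 keeps participants who stop treatment in the study and assesses them where feasible. Section 3.1 does not withdraw those started on remdesivir, and 5.2.3 goes on following those started on other COVID-19 treatments. The mTOR sentence of 5.2.3 and section 5.6 withdraw or remove participants, all in windows ending before Day 14, and neither says whether the Day 14 score is still taken. The bar in 4.5 applies only to withdrawal of consent.

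**The case against.** The strongest reply is that few participants are affected. Dosing is blinded (5.8), treatment stoppers stay under assessment (4.4.2), follow-up continues wherever the resident goes (4.4.1), and only dosed residents who leave within two weeks have their Day 14 score carried. A visible effect needs something like a threefold difference between arms; at 5% against 8%, set A paths give 5.1% (uniform) and 4.2% (mild), with simulation error of about 0.6 points. This stands as a limit on size.

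The second reply is that imputation was tested on favourable ground. With withdrawal unrelated to outcome, leaving withdrawals out also keeps type I error near 5%, although it departs from analysing everyone randomised. When withdrawal was made three times likelier for Day 14 levels 4-7 (5% against 15%), imputation was still better under uniform controls (odds ratio 1.03 against 1.21). Under the mild distribution it barely differed (1.06 against 1.08). So its near-nominal results are conditional on the simulated mechanism.

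Third, the removal clauses are narrow and worded identically for both arms, so they create no arm difference by themselves. A reader might infer that they contradict the intention-to-treat statement. They do not: leaving the study is not leaving the analysis, and 8.2 keeps a dosed withdrawal in through the carried score. A reader might also infer that carry-forward alone decides the outcome once consent is withdrawn, but 10.1 allows vital status to be sought, with permission, from those who revoke authorisation. Finally, because 4.4.4 counts death as withdrawal, a reader might fear that deaths are carried at their last living score. Death is itself a category of the scale (2.1), so the natural reading scores it as death.

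**Conclusion.** The point holds as a weakness worth correcting. On the plan's own picture of the disease, an early score is a poor stand-in for the Day 14 score, and the plan has no second line of defence for its primary endpoint. With equal withdrawal, type I error stays near 5% and the odds ratio is somewhat attenuated. With an assumed 5% against 15%, type I error is about 5-8%, depending on patient paths and control distribution.

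A reader might infer that the rule favours Fisetin or costs power in general. Neither is supported: the documents give no withdrawal rate, predict no arm difference, and under milder outcomes the error can run against the drug at no cost in power. All withdrawal rates, paths and non-uniform distributions above are assumptions. Confidence is medium, because the size depends on rates that the documents do not give.

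**What to change.** For the primary Day 14 analysis, replace carry-forward with multiple imputation or a longitudinal proportional-odds model. Use the daily Day 0-14 scores (7.3), arm and baseline covariates. Apply it to every randomised participant without a Day 14 score, including undosed and lost participants, and use vital status where it is known. Report the number of imputed scores by arm. Add a sensitivity analysis for departures from missing at random, for example shifting imputed Fisetin-arm scores one category worse, and keep carry-forward as a secondary check.

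Reconcile 4.4.2, 5.2.3, 5.6 and 8.2 so that outcome scoring continues after study drug stops unless consent is withdrawn. This alters no drug restriction and no rule for stopping study drug.

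The cost is protocol and SAP wording, modest analysis work, and chart abstraction for a few participants. The main downside is the missing-at-random assumption, given daily scores that are recorded only where feasible. With an assumed 60% of daily scores recorded, imputation still gave 4.6-4.7% type I error and an odds ratio of 1.00 on two path sets, against 6.2-7.9% with carry-forward. Section 8 already plans mixed models for the senescence markers, so the approach is not foreign to the plan.

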Based upon review of the published literature and our pre-clinical data, we do not anticipate the occurrence of serious adverse events with the prescribed regimen in this study. We have identified a variety of drug-drug interactions (*e.g.*, current use of warfarin) for which we established exclusion criteria or modification plans to minimize associated risks. We could find no reports of Fisetin toxicity in the literature. Some flavonols have been associated with DNA damage *in vitro*, but Fisetin exerts little or no genotoxic effects. To the contrary, Fisetin has been noted to be anticarcinogenic. Indeed, we found that chronic Fisetin administration delays cancer in mice and increases remaining lifespan in old mice as well as increasing lifespan of DNA damage/ genotoxicity highly-prone  $Ercc1^{-/\Delta}$  mice by over  $17\%^{59}$ . Since up to 50% of most mouse strains die from cancers, this shows that the beneficial effects of Fisetin on such procarcinogenic factors as senescent cell burden and tissue chronic inflammation appear to more than counteract any theoretical effects of flavonol-associated genotoxicity. **Fisetin actually reduces cancer risk**, as opposed to increasing it.

Overall, we do not anticipate substantial risk from the natural product, Fisetin, which is present in many foods, including cucumbers, strawberries, and other fruits and vegetables, albeit at levels lower than will be used here. CoV infection causes 25 to 50% mortality in nursing home patients. Thus, the risks of using this drug are likely minimal compared to the anticipated benefits for nursing home patients with a limited life expectancy, even without CoV infection.

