# 3.3 Duration of Participation

The study is estimated to complete enrollment within 18 months from study initiation; however, enrollment will remain open until the study goal is met. The duration of this study for each subject will be a maximum of 6 months. Study treatment will take approximately 4 out of 10 days. Subjects will be followed for up to 6 months or death, whichever comes first, including any available laboratory and chest imaging results if done as part of nursing home care. This will be done through study staff and health care providers in the nursing home or, if transferred to hospital, another facility, or home, by study staff contacting patients, their LAR, and/or their health care providers daily if feasible from Days 0 to 14 and at Days 30, 90 and 180 ( $\pm 14$ ; unblinding) after Fisetin vs. placebo was commenced if feasible, or from nursing home or hospital records. Adverse event reporting will be collected daily if feasible from the time of consent through Day 14. Adverse events will be assessed again at Days 30, 90 and 180, if possible. Subjects will not be required to return to the nursing home if discharged home or to another care setting.

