### **4.4.1.** Study Completion:

For each subject in the study, the end of study will be reached when treatment and post-treatment safety follow-up periods have been completed, including follow-up of patients discharged from the nursing home to home, other care settings, or hospital, *i.e.* subjects will be followed if

feasible, irrespective of their location, by telephone or in person until the 180 ( $\pm$ 14) day follow-up visit or death.

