# 4.4.4. Premature Withdrawal from Study:

Subjects or their LAR may voluntarily withdraw from the study for any reason at any time. Subjects are considered withdrawn if they or their LAR state an intention to withdraw further participation in all components of the study or if subjects die. If premature withdrawal occurs for any reason, the reason for premature withdrawal from the study, along with who made the decision (subject, LAR, responsible nursing home physician, physician's assistant, or nurse-practitioner, investigator) will be recorded in the CRF.

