### 4.4.6. Subject Replacement:

Subjects withdrawn (due to withdrawal of consent) from the study will not be replaced and analytic methods will be by intent-to-treat.

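### Carry-forward in section 8.2 has no exemption for death, so a participant who dies can keep a living MDS function or cognition score to Day 180

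*Combined protocol and SAP*

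**What the plan says.** - **Section 8.2, Statistical Methods:** "Subjects who withdraw early but received at least some treatment will have their last known values carried forward until they complete the study", with completion put at Day 180±14. The sentence names no endpoint and does not mention death.
- **Section 4.4.4, Premature Withdrawal from Study:** subjects count as withdrawn if they or their representative "state an intention to withdraw further participation in all components of the study or if subjects die".
- **Section 3.5, Secondary Study Endpoints:** three endpoints come from the MDS: cognition (section C), "function status/activities of daily living (from MDS Section G") and functional abilities/frailty (section GG). None is given a level for death.
- **Section 3.3, Duration of Participation:** "Subjects will be followed for up to 6 months or death, whichever comes first".
- **Section 4.4.1, Study Completion:** follow-up runs to the 180 (±14) "day follow-up visit or death".
- **Section 4.4.6, Subject Replacement:** "Subjects withdrawn (due to withdrawal of consent) from the study will not be replaced". Here, as in 4.5, withdrawal is limited to withdrawn consent. Section 8.2 has no such limit.
- **Sections 6.2 and 6.5 to 6.7, and Appendix 2:** an MDS record is taken at baseline and at Days 30, 90 and 180, as available. The baseline and Day 30 entries are the latest record on file, which may be up to 100 days old.

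**The concern.** Carry-forward assumes that a person who left would have stayed at the last observed level. For someone who has died, that level does not exist. If the rule is applied as sections 4.4.4 and 8.2 read together, a death enters the Day 180 function and cognition comparisons as a living person with a stable score.

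The last score is often an old one. A participant who dies before a new MDS is completed has only the baseline record to carry, and that record can predate the infection. Such a death counts as no decline, which is better than a survivor who got worse.

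If mortality differs between arms, the comparison is then tilted towards the arm with more deaths. A drug that saved lives would be penalised on function, and one that cost lives would be flattered.

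**Working it through.** **The plan's own figure.** The plan gives no figure for the MDS endpoints. Its only power figure (section 8.1: 75 per arm, log odds ratio 0.81, two-sided 0.05, controls spread equally over seven levels, 80%) is for the 7-point scale. Whitehead's proportional-odds formula is power = Φ(|log OR| × √(N(1 − Σp̄³)/12) − 1.96), where p̄ is the mean of the two arms' category probabilities. With N = 150 and Σp̄³ ≈ 0.024, it gives Φ(0.81 × √(150 × 0.976/12) − 1.96) = Φ(0.87) ≈ 80.8%. The figure reproduces, and this point does not affect it.

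**Does the rule reach deaths?**
1. Section 8.2 applies to treated subjects who withdraw early. Dosing is planned for the day of randomisation if possible (section 6.1), so few should fall outside it.
2. Section 4.4.4 makes death a form of withdrawal.
3. Sections 4.4.6 and 4.5 add the consent limit when they mean only that; section 8.2 does not.
4. Section 8.2 fixes the end of carrying at Day 180±14, not at death.
5. Against this, sections 3.3 and 4.4.1 treat death as the end of follow-up, which would leave nothing to carry.

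The first reading gives dead participants a living MDS score. The second leaves the MDS endpoints with no rule for death, because the secondary-endpoint plan (8.2.1 in the contents) gives these endpoints no method.

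**How many people?** These are illustrations, not projections. Section 1.6 states that "CoV infection causes 25 to 50% mortality in nursing home patients". Applied equally to 150 randomised, that is 0.25 × 150 ≈ 38 to 0.50 × 150 = 75. If the design odds ratio of 2.25 is also applied to death (an assumption):

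| Control mortality | Fisetin mortality | Deaths, control + fisetin |
|---|---|---|
| 1/7 (power model, Day 14) | 6.9% | 10.7 + 5.2 ≈ 16 |
| 25% | 12.9% | 18.8 + 9.7 ≈ 28 |
| 50% | 30.8% | 37.5 + 23.1 ≈ 61 |

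**Size and direction.** Let m be mortality in an arm, d the mean decline in survivors (equal in both arms), and c the decline already present in the record carried for those who die.

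Mean decline in an arm = (1 − m)d + mc.

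Apparent advantage of the arm with more deaths = (difference in m) × (d − c).

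With d = 4 (assumed; the plan names MDS items but no derived score):
- c = 0, gap of 5 percentage points: 0.05 × 4 = 0.2 points.
- c = 0, gap of 15 points, as 25% v 40%: 0.75 × 4 = 3.0 and 0.60 × 4 = 2.4, a difference of 0.6 points.
- c = 4, same mortality: 4.0 in both arms, a difference of 0.
- c = 6, same mortality: 3.0 + 1.5 = 4.5 and 2.4 + 2.4 = 4.8, so the arm with more deaths looks 0.3 points worse.

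**In standardised terms.** A simulation of 4,000 trials with 75 per arm assumed that survivors lose 0.5 baseline SD, that the SD of change is 0.7, that the drug has no effect on function, that the dead are carried at baseline, and that the mortality odds ratio is 2.25 in favour of fisetin. Fisetin then looks 0.06 SD worse at 25% control mortality and 0.10 SD worse at 50%. The formula agrees: (0.25 − 0.129) × 0.5 = 0.06 and (0.50 − 0.308) × 0.5 = 0.10. A Mann-Whitney test at 5% rejects in 6% and 8.5% of trials. With death ranked worst it rejects in 24% and 56%, because that analysis also counts the survival difference.

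**The case against.** The strongest reply is that no sentence says MDS scores are carried past death. The result comes from joining a definition in the withdrawal section to an analysis sentence that directly follows the primary 7-point model. The secondary-endpoint plan never mentions carry-forward; for senescent-cell markers it uses mixed models on all available data. Section 4.4.3 describes withdrawal as withdrawn consent, and 3.3 and 4.4.1 end follow-up at death. The Day 180 horizon does not settle the matter, because the 7-point scale is also recorded to Day 180. This stands to the extent that the result is a consequence of the text and not a declared method. It does not remove the gap, since the rival reading leaves death without a rule.

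A reader might infer more than the documents support:
- **That every withdrawn subject is covered.** The rule is limited to those who had some study treatment.
- **That the primary endpoint is corrupted.** Death is the worst level of the 7-point scale (section 2.1). A recorded death is itself the last known value and carries forward correctly.
- **That 25 to 50% of Day 180 MDS values would belong to the dead.** That range describes infected nursing home residents in general. The power model places 1/7 of controls in the death category at Day 14.
- **That the arm with more deaths must look better.** This needs c < d. Days 30 and 90 also collect the MDS, and section 6.1 collects every MDS record during participation, so some who die will carry a record that already shows decline.

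**Conclusion.** The point holds as a conflict in the text with a real consequence if followed literally. Sections 4.4.4 and 8.2 together give a treated participant who dies a living MDS score to Day 180, while sections 3.3 and 4.4.1 point the other way.

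The affected endpoints are secondary: cognition, ADL and functional abilities. The bias is (mortality difference) × (d − c). It is 0.2 to 0.6 points in favour of the arm with more deaths for an assumed 5 to 15 percentage-point gap, d = 4 and deaths carried at baseline, or 0.06 to 0.10 SD under the simulation's assumptions. It is zero if mortality is equal or the carried decline matches that of survivors, and it reverses if the carried decline is larger. Where there is no true difference in function among survivors, as in these illustrations, the rule alone sets the sign of the comparison. That justifies correcting it, although the amounts are modest.

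**What to change.** 1. State in section 8.2 that carry-forward does not apply after death for any endpoint without a death level.
2. Reconcile sections 4.4.1, 4.4.4, 4.4.6 and 8.2 so that death is either withdrawal or end of follow-up throughout, and say which kinds of withdrawal the carry-forward rule covers.
3. Confirm that death is scored as the worst level of the 7-point scale at every visit on or after the date of death.
4. Pre-specify how death enters the three MDS endpoints. One choice is a ranked composite in all randomised participants with death as the worst rank, and a survivors-only analysis as supportive. A while-alive or survivor estimand is also defensible if its limits are stated.

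The cost is wording only; no new data are needed. The downside of the composite is that it mixes death and function, so a difference may come from mortality alone. Deaths by arm and function among survivors must therefore be reported separately beside it.
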